9.2.4.1 Critical Data

The QC plan requires datasets be classified as critical or non-critical. As the primary end-point of this study are AEs and SAEs the analysis datasets considered critical are subject level dataset (ADSL) and the adverse events analysis dataset (ADAE). As these are related to the primary objectives these datasets will be double programmed per the QC Plan. In addition, double programming will be used to check the ADPP dataset.

9.2.5 ADaM Datasets and Metadata

The analysis datasets will be generated in accordance with Clinical Data Interchange Standard Consortium (CDISC) Analysis Data Model (ADaM) Version 2.1. The following ADaM datasets will be prepared:

Table 5 ADaM datasets

ADaM Dataset Name	Description
ADSL	Subject Level Analysis Dataset
ADAE	Adverse Events Analysis Dataset
ADEG	ECG Analysis Dataset
ADLB	Laboratory Test Results Analysis Dataset
ADPC	Pharmacokinetic Concentrations Analysis Dataset
ADPP	Pharmacokinetic Parameters Analysis Dataset
ADVS	Vital Signs Analysis Dataset

ADaM compliant datasets will be delivered to the sponsor. A define.xml file Version 2 with the corresponding metadata will be included. Analysis results metadata are excluded.

9.3 Software

The statistical analysis and reporting will be done using SAS® for Windows™ Version 9.4 or higher (SAS Institute, Inc.).

PK parameter calculations will primarily be done using Phoenix® WinNonlin® Version 8.1 or higher (Certara, Inc.). Additional PK computations may be performed in SAS®.

9.4 Statistical Methods

9.4.1 Statistical Outlier Determination

No statistical outlier analysis is planned. PK concentrations that appear to be outliers will be assessed on a case-by-case basis.

9.4.2 Predetermined Covariates and Prognostic Factors

There are no predetermined covariates or prognostic factors.

9.4.3 Hypothesis Testing

No formal hypothesis testing will be done.

9.5 TFL Layout

The layout of Tables, Figures and Listings (TFLs) will be according to the PRA EDS standards and will be provided in Adobe PDF format. Any in-text tables will be provided as RTF tables and in-text figures will be provided as

Format:

- Page size: LETTER
- Data in listings will be sorted by study part, subject number and time point.
- Data in safety and PK concentration tables will be sorted by study part, treatment and time point.
- Column titles will be in title case letters.
- All tables and listings will be in landscape format.
- The treatment labels used in TFL will be as outlined in [Table 3](#), Section 9.2.2.

Any in-text tables will be provided as RTF tables and in-text figures will be provided as PNG files.

10.0 Analysis Sets

Analyses	Randomized Set	Safety Set	Pharmacokinetic Set
Disposition Summaries	✓		
Safety Assessments		✓	
Baseline Characteristics		✓	
Primary Analysis		✓	
PK Concentrations			✓
PK Parameters			✓

10.1 Randomized Set

The all subjects randomized set will consist of subjects who are assigned a randomization number in the study. This set will be used for disposition summaries.

10.2 Safety Set

The safety set will consist of subjects who receive at least one dose of study drug (LY3526318 or placebo). This set will be used for the safety data summaries, baseline characteristic summaries, and PK concentration summaries.

10.3 Pharmacokinetic Set

All participants administered with LY3526318 who have evaluable plasma and/or urine LY3526318 concentrations will be included in the PK analyses. Pharmacokinetic parameter estimates for LY3526318 will be computed using standard noncompartmental methods of analysis.

11.0 Subject Disposition

All disposition data (collected in the SDTM DS domain) will be listed. All subjects who discontinue from the study will be identified.

The number and percentage of subjects randomized, dosed, and members of each analysis set will be presented. The number and percentage of subjects who withdrew from the study prematurely and a breakdown of the corresponding reasons for withdrawal will also be presented.

12.0 Protocol Deviations and Violations

Protocol deviations/violations will be included in the CSR.

13.0 Demographic and Baseline Characteristics

13.1 Demographics

All demographic data as collected during the screenings visit will be listed by subject.

Subject demographics will be summarized descriptively for all subjects by part and treatment. The summary will include the subjects' age (in years), gender, race, ethnicity, weight (in kg), height (in cm), and body mass index (BMI, in kg/m²). Demographics will be summarized for the safety and PK sets.

13.2 Medical History

Medical history will be listed.

13.3 Other Baseline Characteristics

The results of drug and alcohol screen at screening will be listed.

Non-compliance to in- or exclusion criteria (if any) will be listed.

14.0 Concomitant Medications

Concomitant medications will be listed by subject. Medications with an end date prior to the first dose of study drug will be considered prior medications and will be identified as such in the listing. If a partial date allows a medication to be considered concomitant it will be categorized as such.

Concomitant medications will be coded according to the WHODrug dictionary (WHODrug Global B3 SEP2019).

15.0 Treatment Compliance and Exposure

All exposure data will be listed by subject.

16.0 Pharmacokinetic Analyses

16.1 Pharmacokinetic Variables

16.1.1 Plasma Variables

16.1.1.1 Concentrations

- Plasma concentrations of LY3526318 (in mass/volume units)
- Plasma concentrations of LSN3528305 (in mass/volume units)

16.1.1.2 Parameters

- Plasma PK Parameters for LY3526318 as defined in [Table 6](#).
- Plasma PK Parameters for LSN3528305 as defined in [Table 6](#).

Table 6 Plasma PK Parameters

Parameter* (unit)	Description	SAD	MAD Day 1	MAD Day 14	SAS Programming Notes
C_{max} (ng/mL)	Maximum plasma concentration. Observed peak analyte concentration obtained directly from the experimental data without interpolation	✓	✓	✓	Cmax from WNL
T_{max} (h)	Time to maximum plasma concentration. First observed time to reach peak analyte concentration obtained directly from the experimental data without interpolation, in hours (h)	✓	✓	✓	Tmax from WNL
λ_z (/h)	Terminal phase rate constant calculated by linear regression of the terminal log-linear portion of the concentration vs. time curve. Linear regression of at least three points and an adjusted r^2 greater than 0.80 are required to obtain a reliable λ_z	✓	(✓)	(✓)	Lambda_z from WNL If Rsq adjusted ≤ 0.80 then the parameter is flagged (but not excluded from descriptive statistics)
$t_{1/2}$ (h)	Terminal phase half-life expressed in time units. Percent extrapolation less than or equal to 20% and r^2 greater than 0.80 is required to obtain a reliable $t_{1/2}$	✓	(✓)	(✓)	HL_Lambda_z from WNL If Rsq adjusted ≤ 0.80 then the parameter is flagged (but not excluded from descriptive statistics)
AUC_{0-last} (ng·h/mL)	Area under the concentration-time curve (time 0 to time of last quantifiable concentration)	✓			AUClast from WNL
AUC_{0-inf} (ng·h/mL)	Area under the plasma concentration-time curve (time 0 to infinity). Percent extrapolation less than or equal to 20% is required to obtain a reliable AUC_{0-inf} , in ng·h/mL	✓			AUCINF_obs from WNL If $AUC_ \%Extrap_obs > 20\%$ and Rsq adjusted ≤ 0.80 then parameter is flagged (but not excluded from descriptive statistics)
AUC_{0-24} (ng·h/mL)	Area under the concentration-time curve (time 0 to 24h), in ng·h/mL	✓	✓		
$AUC_{0-24,ss}$ (ng·h/mL)	Area under the plasma concentration-time curve over the dosing interval (24h) at steady state, in ng·h/mL			✓	AUCtau from WNL where tau is equal to 24 h, if missing for a subject then AUC at nominal time 24 h from summary file is used for AUC_{0-tau}

Parameter* (unit)	Description	SAD	MAD Day 1	MAD Day 14	SAS Programming Notes
CL/F (L/h)	Apparent oral clearance, calculated as Dose/AUC _{0-inf} for the SAD regimens or Dose/AUC _{0-tau} for the MAD regimens on Day 14 For parent compound (LY3526318) only, in L/h	✓		✓	CL_F_obs or CLss_F from WNL respectively. If AUC_%Extrap_obs >20% and Rsq adjusted ≤ 0.80 then parameter is flagged (but not excluded from descriptive statistics)
Vz/F (L)	Apparent volume of distribution calculated as (CL/F)/λ _z For parent compound (LY3526318) only, in L	✓		✓	Vz_F_obs from WNL.
AR _{AUC}	Accumulation ratio calculated as: $AR_{AUC} = \frac{AUC_{0-24,SS}}{AUC_{0-24,Day\ 1}}$			✓	Calculated in SAS by dividing the AUC _{tau} from WNL on Day 14 by the AUC ₀₋₂₄ on day 1.
LI	Linearity index factor of pharmacokinetics after repeated administration $LI_{AUC} = \frac{AUC_{0-24,SS}}{AUC_{0-inf,Day\ 1}}$			✓	Calculated in SAS by dividing the AUC _{tau} from WNL on Day 14 by the AUC _{INF_obs} from WNL on day 1 if feasible (i.e., if AUC _{INF_obs} can be estimated).

Note: AUCs will be calculated using the linear up / log down method, expressed in units of concentration x time.

✓ = Will be calculated. (✓) = Will only be calculated if feasible.

*) In End-of-text TFL, subscript will not be used.

16.1.2 Urine Variables

16.1.2.1 Concentrations

- Urine concentrations of LY3526318 and LSN3528305 measured in the 0-24h collection interval (Part A only) in mass per volume units

16.1.2.2 Amounts Excreted

The Amount of LY3526318 and LSN3528305 excreted (Ae) in urine in the 0-24h collection interval (Part A only) will be calculated as:

$$Ae_{0-24} = C \times V$$

Where, C is the concentration of LY3526318 or LSN3528305 measured in the 0-24h collection interval and V is the volume of urine collection.

16.1.2.3 Parameters

- PK Parameters for LY3526318 and LSN3528305 as defined in Table 7

Table 7 Urine PK parameters

Parameter	Description	SAS Programming Notes
Ae_{0-24} (mg)	
Amount of drug excreted unchanged into urine in the 0-24h collection interval in mg, calculated as
 $Ae_{0-24} = C \times V$ 
where, C is the concentration of LY3526318 measured in the 0-24h collection interval and V is the volume of urine collection
	Calculated by multiplying the urine concentration measured in the 0-24h urine collection interval sample in ng/mL times the volume of the sample in mL
Fe_{0-24} (%)	
Fraction (%) of the administered dose excreted unchanged into urine, calculated as
 $Fe_{0-24} = \frac{Ae_{0-24}}{Dose} \times 100\%$	Calculated by dividing the amount excreted by the (planned) dose of LY3526318 administered.
CL_R (L/h)	
Renal clearance calculated as
 $CL_R = \frac{Ae_{0-24}}{AUC_{0-24}}$ 
Where Ae_{0-24} is the amount excreted defined above and AUC_{0-24} is the area under the plasma concentration-time curve for time 0 to 24h as defined in Table 6 above.
	Calculated by the dividing the amount excreted by the area under the plasma concentration-time curve for time 0 to 24h as obtained from WNL

16.2 Pharmacokinetic Summaries

16.2.1 Pharmacokinetic Concentrations

Plasma concentrations for LY3526318 below the quantifiable limit (BQL) will be set to $\frac{1}{2}$ lower limit of quantification (LLOQ) in the computation of descriptive statistics of concentration values. Descriptive statistics (number of subjects, arithmetic mean, standard deviation, coefficient of variation, median, minimum, maximum, geometric mean, and geometric CV) will be used to summarize the plasma concentrations by treatment at each scheduled time point. If over $\frac{1}{2}$ the subjects in a given cell have values BQL then the descriptive statistics will not be presented and will instead display as BQL for the mean and minimum. All other statistics except the maximum will be missing.

Linear and semi-logarithmic plots of the geometric mean plasma concentration versus scheduled sampling time will be presented by part showing all fasted treatments in a single figure.

Separate geometric mean linear and semi-logarithmic plots will show the effect of food given at the same dose (fed versus fasted) for the 30 mg and 200 mg cohorts, that is: Cohort 3 Period 2 and Cohort 6 Period 1 for 30 mg and Cohort 4 Periods 1 and 2 for 200 mg. Also separate geometric mean linear and semi-logarithmic plots will show the effect of food and the timing of food given at the 100 mg dose level (predose, 30 min postdose and 1 hour postpose and fasted) from Cohort 10 Periods 1-3 and Cohort 3 Period 1, respectively. These plots will show time in hours. The plots will match the summary table results and will not have an observation at a given time point if more than half of the subjects have values BQL.

For the multiple dose part, geometric mean profiles will be presented for all treatments in a single plot with a Day 1 and Day 14 profiles superimposed. In addition, linear geometric mean through plasma concentrations versus scheduled sampling time will be presented. These trough plots will include all trough concentrations from time zero on Day 1 up to 24 hours after dosing on Day 14.

Linear and semi-logarithmic plots of the combined individual plasma concentration versus actual sampling times will be provided by treatment, showing all subjects that received active treatment in one plot for each dose level. These plots will show time in hours and will use the BQL handling procedure described below for "Pharmacokinetic Parameters". For the MAD Part, these plots will be presented for Day 1 and Day 14 separately.

Linear and semi-logarithmic plots of the individual concentration by actual sampling time will be provided by subject (one subject per plot, 6 plots per page). These plots will show time in hours and will use the BQL handling procedure described below for "Pharmacokinetic Parameters".

Individual plasma concentration data will be presented together with descriptive statistics by treatment.

Individual urine concentrations will be listed together with the sample weight/volume and the derived excretion parameters.

16.2.2 Pharmacokinetic Parameters

Plasma PK parameters for LY3526318 will be estimated using non-compartmental methods with WNL.

The plasma PK parameters will be estimated from individual concentration-time data. In estimating the PK parameters, BQL values at the beginning of the profile will be set to zero. BQL values that occur after the first quantifiable point will be considered missing. Values that are embedded between BQLs, or quantifiable values occurring after two or more BQLs, will be set to missing at the discretion of the pharmacokineticist. Actual sampling times will be used in all computations involving sampling times. If the actual time or dose time is missing, the scheduled time may be substituted in order to calculate the PK parameter.

The points to be included in the λz range will be determined by the pharmacokineticist after inspection of the semi-log concentration-time profiles. At least 3 points will be required to be used. The C_{max} data point will not be included.

Descriptive statistics (number of subjects, arithmetic mean, geometric mean, standard deviation, arithmetic and geometric CV, median, minimum, and maximum) will be used to summarize the calculated plasma PK parameters by treatment. For T_{max} , only median, min and max will be presented.

Urine PK parameters will be derived in SAS. Descriptive statistics (number of subjects, arithmetic mean, geometric mean, standard deviation, arithmetic and geometric CV median, minimum, and maximum) will be used to summarize the calculated urine PK parameters by treatment.

16.2.2.1 Dose-Proportionality

Dose proportionality will be explored for C_{max} and AUC_{0-inf} (for SAD) or $AUC_{0-24,ss}$ (for MAD) using the power model as described by Smith et al, 2000. If AUC_{0-inf} cannot be calculated in many profiles rendering the relationship suspect, AUC_{0-24} will be used instead. In the power model, the \log_e -transformed parameters (Y) are assumed to be linearly related to the \log_e -transformed Dose:

$$\log_e Y = \beta_0 + \beta_1 \cdot \log_e (Dose)$$

Results will be presented both in a table and graphically. The table will show the results of the dose proportionality assessment as shown in Table 2 in Smith et al, 2000. If the 90% confidence Intervals (CIs) for the dose-normalized ratio of PK geometric mean values (over the full range of doses tested) is included in the interval (0.8, 1.25) dose proportionality can be assumed. The maximum fold dose range in which dose proportionality can be concluded will also be reported.

In the dose proportionality figures, the individual C_{max} and AUC values will be plotted against the dose and the power model fit together with the corresponding 90% prediction limits and an additional line showing the best straight line through the origin (i.e., $Y = \beta \cdot Dose$) will be presented (see Fig 1 in Smith et al, 2000). The equations (showing final parameter estimates) of the best fit power and linear models will be displayed.

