5.1 Overall Design

This is a Phase 1, single-ascending dose (SAD, Part A) and multiple-ascending dose (MAD, Part B) study of LY3526318 in healthy participants. Both parts are randomized, double-blind, and placebo-controlled.

Part A (SAD):

The single-ascending doses of LY3526318 or placebo will be administered, at planned dose levels of 10, 50, 100, 400, 800, and 1000 mg, in 7 cohorts of 8 participants each, except the expanded 100-mg cohort that will include 12 participants (8 female and 4 male) to accommodate a food effect assessment in the female participants only.

Following a screening period of up to 28 days, eligible participants will be confined to the clinical research unit (CRU) from Day -1 until all study assessments are completed on Day 3. A sentinel dosing strategy will be implemented for the first dose level (Cohort 1, 10 mg). Two participants will receive a sentinel dose (1 each with LY3526318 and placebo) and the remaining participants will be administered LY3526318 after review of safety data up to 48 hours postdose. Participants in Cohort 1 will not be stratified by sex, given that sentinel dosing coupled with stratification by sex may compromise blinding. A fixed number of females and males will be randomized in Cohorts 2 and 3 and the participants will be stratified to ensure equal distribution between females and males. The Part A stratification by sex scheme is shown in [Table 5-1](#).

Table 5-1 **Part A Stratification Based on Sex**

Cohort (Planned dose level ^a)	Number of Females Randomized	Number of Males Randomized	Total Participants Randomized
Cohort 1 (10 mg)	Up to 8 ^b	Up to 8 ^b	8
Cohort 2 (50 mg)	4	4	8
Cohort 3 (100 mg)	8 ^c	4	12
Cohort 4 (400 mg)	8 ^c	NA	8
Cohort 5 (800 mg)	8	NA	8
Cohort 6 (1000 mg)	8	NA	8
Cohort 10 (100 mg)	8 ^d	NA	8

Abbreviation: NA = not applicable.

- ^a Doses may be adjusted based on data obtained in previous study cohorts.
- ^b Cohort 1 will not have a defined stratification by sex scheme. Eight participants will be randomized including males and/or females.
- ^c Female participants in Cohorts 3 and 4 will receive study drug in fasted and fed conditions, separated by a washout period of at least 1 week.

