Modeling of preclinical data in GastroPlus™ suggests that the bioavailability of LY3526318 may increase by approximately 3- to 5-fold when administered with a high-fat meal, relative to administration in the fasted state. Consequently, the 100-mg cohort (females only) was chosen to explore the effect of food administration, considering that even if a 5-fold increase in exposure is observed, it would not exceed the exposure at the maximum planned dose of 1000 mg. The 400-mg dose was chosen because even if there was a 5-fold increase in exposure, it would provide acceptable margins of safety of 5x and 10x for the NOAEL in female rats and monkeys respectively, based on dose multiples. Of note, there were no findings for either female rats or monkeys in the toxicology studies, hence the NOAEL is the maximum administered dose in those studies.

Thus, the proposed doses for both the SAD and MAD portions of the study are anticipated to be in the target engagement dose range, while providing adequate margins of safety to address the study objectives.

6 Study Population

Eligibility of participants for the study will be based on the investigator's judgment on results of screening medical history, physical examination, vital signs, clinical laboratory tests, and electrocardiogram (ECG). The nature of any conditions present at the time of the physical examination and any pre-existing conditions will be documented.

Screening may occur up to 28 days prior to enrollment.

Prospective approval of protocol deviations to recruitment and enrollment criteria, also known as protocol waivers or exemptions, is not permitted.

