6.2 Randomization

A randomization schedule was generated by the EDS Biostatistics department of PRA for all cohorts except Cohort 10 according to the study specific Randomization Specifications created by then PRA biostatistician and approved by the Sponsor.

Part	Cohort	Period	Planned Treatment [#]	Actual Dose [#]	♀	♂	Stratified by sex
A	1a (sentinel)	1	10 mg LY3526318 or Placebo	10 mg	2		No
	1b	1	10 mg LY3526318 or Placebo	10 mg	6		No
	2	1	50 mg LY3526318 or Placebo	50 mg	4	4	Yes
	3	1	100 mg LY3526318 or Placebo	100 mg	8	4*	Yes
		2	100 mg LY3526318 or Placebo fed	30 mg	8		NA
	4	1	400 mg LY3526318 or Placebo	200 mg	8		NA
		2	400 mg LY3526318 or Placebo fed	200 mg	8		NA
	5	1	800 mg LY3526318 or Placebo	300 mg	8		NA
	6	1	1000 mg LY3526318 or Placebo	30 mg	8		NA
	10 (additional)	1	100 mg LY3526318 Fed standardized high fat meal to start 30 minutes prior to dose administration	100 mg	8		NA
		2	Fasted at least 8 hours predose with a standardized high fat meal administered 30 minutes post dose	100 mg			
		3	Fasted at least 8 hours predose with a standardized high fat meal administered 1 hour post dose	100 mg			
	11 (additional)	1	TBD mg LY3526318 or Placebo	NA	8		NA
B	7	1	100 mg LY3526318 or Placebo QD	30 mg	8		NA
	8	1	400 mg LY3526318 or Placebo QD	60 mg	8		NA
	9	1	Up to 1000 mg LY3526318 or Placebo QD	100 mg	8		NA
	12 (additional)	1	TBD mg LY3526318 or Placebo QD	NA	8		NA
	13 (additional)	1	TBD mg LY3526318 or Placebo QD	NA	8		NA
*) Doses may be adjusted based on data obtained in previous study cohorts, see actual dose column for the adjusted doses.							
*) As a result of exposures found in the interim PK data after Cohort 2 being higher than expected, it was decided not to dose male subjects with a 100 mg dose in Cohort 3 and therefore the number of subject in this cohort was also 8.							
NA=not applicable, TBD=to be determined.							

Replacement subjects will receive the same randomization number as the subject to be replaced increased by 1000 and will be administered the same.

In Cohorts 3 and 4 the female subjects will be dosed in a 2nd period in which they were to receive the same treatment under fed conditions. After evaluation of the interim PK results, it was decided to reduce the dose level of Period 2 for Cohort 3 to 30 mg under fed conditions.

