9.2.2 Treatment/Subject Grouping

In summary tables, data will be presented by study part and treatment.

Table 3 Part, Cohort and Treatment Labels

Label	Grouping
Study Part	Part A (SAD) Part B (MAD)
Cohorts	Part A: 1-6 and 10 Part B: 7-9
Planned Treatments	Part A (SAD): – Placebo – Placebo fed – 10 mg LY – 50 mg LY – 100 mg LY – 30 mg LY fed – 200 mg LY – 200 mg LY fed – 300 mg LY – 100 mg LY fed (-30 min) – 100 mg LY fed (+30 min) – 100 mg LY fed (+60 min) Part B (MAD): – Placebo QD – 30 mg LY QD – 60 mg LY QD – 100 mg LY QD

LY = LY 3526318; QD = once daily

For subjects for which the actual treatment received does not match the planned treatment, the treatment actually received will be used for the analysis, in any summaries or analysis. In case this leads the number of subjects receiving those actual treatments being less than 2, the data for these subjects will only be listed and not included in any summaries or analyses.

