16.2.2.2 Food Effect

The effect of food and the timing of food will be graphically presented using box-plots showing AUC_{0-24} , C_{max} versus treatment. This will be done in separate plots for the following comparisons:

- 100 mg LY fasted, 100 mg LY QD (Day only), 100 mg LY fed (-30 min), 100 mg LY fed (+30 min), and 100 mg LY fed (+60 min)
- 30 mg LY fasted (Cohort 6 Period 1) and 30 mg LY fed (Cohort 3 Period 2)
- 200 mg LY fasted 200 mg LY fed (Cohort 4 Periods 1 and 2)

In addition, for the 200 mg dose level (i.e. Cohort 4 Periods 1 and 2), an analysis of variance (ANOVA) will be performed on AUC_{0-24} and C_{max} using the SAS PROC MIXED to estimate the geometric mean ratio and corresponding 90% CIs. Dose normalized PK parameters will be natural logarithm transformed prior to the analysis. The model will include fixed effects for food consumption status (fasted or fed) and a random effect for subject. From this model the back-transformed least-squares means (LSMeans) for each treatment and their ratio will be estimated. The ratio of least-squares geometric means between fed and fasted condition and the corresponding 90% CI will be presented.

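### Does SAP 16.2.2.1 need to name the Part A profiles, or adjust for sex, in the exploratory dose-proportionality model?

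*SAP*

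**What the plan says.** SAP 16.2.2.1 fits the power model to Cmax and AUC0-inf in Part A, with AUC0-24 as fallback. Log dose is the only regressor. Proportionality is accepted if the 90% CI for the dose-normalised ratio "over the full range of doses tested) is included in the interval (0.8, 1.25) dose proportionality can be assumed". The section also asks for the maximum fold range over which proportionality holds, and for plots of individual values against dose with the fit and 90% prediction limits. It names no cohorts or periods.

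By the actual-dose column of SAP 6.2, Part A has fasted profiles at 10, 30, 50, 100, 200 and 300 mg, and fed profiles at 30, 100 and 200 mg.

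Other places bear on which profiles enter:
- SAP 16.2.1: the mean concentration plots "will be presented by part showing all fasted treatments in a single figure".
- SAP 16.2.2.2: the food comparison names its sources, for example "30 mg LY fasted (Cohort 6 Period 1) and 30 mg LY fed (Cohort 3 Period 2".
- SAP 9.2.2, Table 3: the Part A labels include "50 mg LY – 100 mg LY – 30 mg LY fed – 200 mg LY", with no fasted 30 mg entry.
- Protocol 5.5: bioavailability "may increase by approximately 3- to 5-fold when administered with a high-fat meal".

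On sex, Protocol Table 5-1 says of Cohort 1: "Eight participants will be randomized including males and/or females". Cohort 2 (50 mg) has four men and four women. After Cohort 2, "it was decided not to dose male subjects with a 100 mg dose in Cohort 3", and higher doses are female only. SAP 9.4.2 says: "There are no predetermined covariates or prognostic factors".

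**The concern.** Read alone, 16.2.2.1 leaves the data set open. Its output is assigned only to the PK set, and SAP 10.3 does not exclude fed periods from that set. The authors wrote the fasted restriction for the mean plots but not here. Fed profiles in a model without a food term would tilt the slope and inflate the residual variance, so proportional kinetics could be reported as failing. The gap in Table 3 adds a practical worry: outputs must use its labels (SAP 9.5), so fasted 30 mg data could be dropped or merged with the fed arm.

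The second worry is confounding. With men only at the two lower doses, a sex difference in exposure would load onto the dose slope, and no covariate is planned. At stake is a secondary pharmacokinetic description. The primary safety conclusions are untouched.

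**Working it through.** The SAP states no precision or power figure for this analysis, so there is none to reproduce.

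**Inputs.** Allocation of 3:1 gives 6 active participants in each of Cohorts 1-6 (Cohort 3 as executed, women only). The fasted set is 6 doses × 6 = 36 profiles, with sum of squares of log dose Sxx = 47.7. Fed profiles are 6 at 30 mg, 6 at 200 mg and 8 × 3 = 24 at 100 mg (Cohort 10). True kinetics are set exactly proportional (slope 1). Fed profiles are shifted by ln F, with F = 3 or 5 from Protocol 5.5, a preclinical projection and not an observed value.

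**Rule in slope terms.** The ratio over the range is 30^(b−1), so the 90% CI for b must lie within 1 ± ln 1.25/ln 30 = 1 ± 0.0656.

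**Mildest pooled set (30 and 200 mg fed, n = 48), F = 3, no subject variability.**
- The pooled mean log dose is 4.240 and Sxx = 58.7.
- Slope shift = ln 3 × 6 × [(3.401 − 4.240) + (5.298 − 4.240)]/58.7 = 1.0986 × 1.313/58.7 = 0.025.
- Residual SS = (ln 3)² × [36 × 12/48 − 1.313²/58.7] = 1.207 × 8.971 = 10.83, so s = √(10.83/46) = 0.485.
- 90% half-width = 1.679 × 0.485/√58.7 = 0.106.
- Ratio 30^0.025 = 1.09, CI 30^(0.0246 ± 0.1063) = 0.76-1.56. The rule fails.

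| Fed profiles added | n | Slope, F = 3 / 5 | Ratio (90% CI), F = 3 | F at which the rule is lost |
|---|---|---|---|---|
| 30 and 200 mg | 48 | 1.025 / 1.036 | 1.09 (0.76-1.56) | 1.73 |
| plus Cohort 10 pre-dose meal | 56 | 1.059 / 1.086 | 1.22 (0.82-1.81) | 1.51 |
| all fed | 72 | 1.103 / 1.151 | 1.42 (0.95-2.11) | 1.39 |

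The last row applies F to the post-dose meals too, for which no multiplier is given.

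**Could pooling create a false pass?** The half-width scales with ln F and does not depend on the true slope. At F = 2 it is 0.106 × ln 2/ln 3 = 0.067 in the mildest set, already above 0.0656. In these noise-free fits pooling at 2-fold or more therefore cannot produce a pass at any slope. The error runs towards not concluding proportionality.

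**Fasted only.** The expected half-width is 1.691 × SD/√47.7. It reaches 0.0656 at a log-SD of 0.268, a CV of about 27%. Simulated pass rates under exact proportionality are 81% at SD 0.15, 43% at 0.2 and about 2% at 0.3. At a true slope of 0.9 they are at most about 0.3% over the same SDs; Protocol 5.4 describes preclinical kinetics as less than proportional. The SDs are assumptions.

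**Sex, fasted only.** Three active men at 50 mg follow from the allocation. The number at 10 mg is unknown (0 to 6). An assumed female/male exposure ratio of 1.4 gives slopes of 1.006, 1.046 and 1.087 with 0, 3 and 6 men at 10 mg; the inverse ratio gives 0.994, 0.954 and 0.913. With 3 men and SD 0.2 the pass rate is 8% unadjusted, 29% with a sex term and 21% in women only. At SD 0.3 all three are below 1%. The slope SE rises 10% (sex term) or 16% (women only) with 3 men at 10 mg, and 37% or 54% with 6.

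**What the SAP implies.** Table 3 lists fed doses as separate treatments, fed placebo is pooled separately (9.1.4), and the Appendix 4 example table for single doses has separate fasted and fed column blocks. The food model in 16.2.2.2 has a subject effect because it uses two periods per person. The power model has none, which suits one profile per person, as the fasted set supplies.

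**The case for a change.** The strongest counter-argument is that an unstated data set is an analyst's choice made after interim data. SAP 3.0 lets planned analyses change without an updated SAP, doses had already been altered on interim results, and one sentence would close the gap. Pooling would also distort the slope and the reported maximum fold range, not only the pass/fail result.

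It stands that the sentence is absent, that it would be cheap, and that the arithmetic is right if pooling occurs. What does not stand is the likelihood of pooling. Nothing in the SAP plans it, the model form does not suit it, and a 3- to 5-fold split between fed and fasted points at the same dose would be plain in the required figures.

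The label gap is real, but SAP 6.2, 16.2.1, 16.2.2.2 and Appendix 4 all identify the 30 mg fasted arm, so a programmer has what is needed. For sex, the confounding is structural, but no document reports a sex difference in exposure. The restriction on men rests on their margin to the NOAEL and on exposures running higher than expected after Cohort 2.

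**Conclusion.** No change to the plan follows. The silence in 16.2.2.1 is missing detail that analysts would fill with fasted single-dose profiles, and writing that down would not alter what is done. The harm is large only under pooling: the rule is lost from about 1.4- to 1.7-fold upward in the three sets tabulated, and at 3-fold the best-case CI is 0.76-1.56. That rests on a projected food effect and on a data set the SAP's structure argues against.

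The rule is also hard to meet without any pooling (about 43% at log-SD 0.2, about 2% at 0.3), in an analysis the SAP calls exploratory, with no formal hypothesis testing and no powering. The Table 3 omission is clerical.

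A sex-adjusted or women-only fit is a matter of preference. Its benefit depends on an assumed 1.4-fold difference, an assumed number of men at 10 mg and low variability; with no men at 10 mg the slope moves by only 0.006. The price is 10-54% in slope SE. The view on sex would change if a sex difference in exposure were documented.
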